12.1.2.3. Outcome Assessment

Subjects will be followed until AEs have either resolved, subjects have returned to their baseline status, or subjects are deemed stable or commensurate with ongoing disease processes. One of 6 AE outcomes listed below must be recorded:

Resolved – The subject has fully recovered from the event and has returned to baseline status without residual observable effects.

Resolved with sequelae – The subject has recovered from the event with some residual observable effects.

Ongoing – The subject has not recovered from the event and observable effects remain, regardless of whether the event is changing or stable and persistent.

Death Due to This Event – The subject died because of the event

Death Due to Other Event – The subject had not recovered from the event at the time of death

Lost to Follow-up – The subject had not recovered from the event at the time of last contact

12.1.3. Reporting Procedures for All Adverse Events

At each visit, all AEs will be documented in response to a general question about the subject's well-being and whether any possible changes in well-being have occurred since the previous visit. Additionally, at each visit, site staff will review subject diary data with the subject and parent/legal guardian/caregiver, to determine if diary entries reflect any AEs. There will be no direct questioning to solicit possible AEs. AEs reported up to 14 days after the final dose of TransCon hGH will be captured. AEs, including SAEs, will be documented through the end of the subject's participation in the trial. All AEs ongoing at the completion of the study or Early Termination Visit must be followed until the event is resolved or deemed stable by the investigator. In this trial, all AEs that are considered mild and not related to investigational product will not be reported on the AE CRF. In addition, the following out-of-range laboratory values—whether or not associated with a titration of the TransCon hGH dose—will not be considered AEs unless they are associated with a clinical sign or symptom: IGF-1, IGF-1 SDS, IGFBP3, IGFBP3. In this trial, IGF-1 and IGFBP3 are pharmacodynamic markers of TransCon hGH therapy and may be used to guide an investigator's recommendation to titrate the TransCon hGH dose. Reportable AEs must be recorded on the appropriate eCRF. Reportable AEs either observed by the investigator or reported by the subject must be recorded regardless of causality.

The following attributes must be documented for each reported AE:

- Subject ID
- Description

- Onset date (if AE was present on Day 1, include whether onset was prior to or after first dose of investigational product)
- Resolution date, if applicable
- Severity
- Causality (relationship to investigational product)
- Outcome
- Action taken
- Determination of “serious” (or not)

Any ongoing AEs from the prior trial will be followed until resolution or stabilization. Any changes to the conditions documented as medical history during the trial and that meet the above AE definition should be recorded as AEs so that a complete safety profile of the investigational product is obtained. See Section 12.2.2 for additional reporting procedures for serious AEs.

Any change from baseline health status that meets the above AE definition and occurs from the time of the first administration of investigational product until the completion of the study or the Early Termination Visit will be recorded as an AE.

Out-of-range laboratory values or test results may constitute AEs if they:

- induce a new/worsening diagnosis, clinical sign, or symptom, or
- require therapy.

Routine titration of chronic, concomitant medications (eg, increase of levothyroxine dose due to interval weight gain and without associated signs/symptoms of overt hypothyroidism) would not be considered as AEs. Whenever possible, an AE should be recorded as a specific diagnosis or syndrome rather than as a sign, symptom, or out-of-range laboratory value. If there is not a diagnosis, the event term should be the clinical sign or symptom. Based on an investigator’s clinical judgement, multiple concurrent symptoms should be grouped together as a single, unifying diagnosis (e.g. headache, fever, cough, and coryza constitute a probable viral upper respiratory tract infection, and this single AE term is more appropriate than listing each symptom as a separate AE).

Care should also be taken to record the most medically appropriate term (eg, hypertension for elevated blood pressure that persists and requires chronic treatment and follow-up, or increased blood pressure for elevated blood pressure that occurs for a limited time and does not persist or require ongoing treatment).

AEs will be documented at the maximum intensity experienced. If a previously recorded AE or condition recorded as part of medical history increases in severity or frequency, it will be recorded as a new AE.

All AEs will be considered ongoing until they have completely resolved or, in the case of a condition recorded as part of medical history, returned to baseline status prior to investigational product administration. At study completion or the Early Termination Visit, all AEs should have a statement regarding resolution.

Any SAE that is determined to be related to the investigational product will be followed until resolution or stabilization.

Any undesirable medical occurrence resulting from an accidental overdose is an AE and should be recorded and reported on the appropriate eCRF page. Regardless of classification as an AE or not, *all* overdoses should be documented, and the subject(s) monitored. Since accidental overdoses with the investigational product could have serious clinical consequences and/or represent a compliance issue, they should be reported to the Medical Expert immediately and evaluated by the Sponsor.

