Note: Any subjects with a history of scoliosis should be monitored for progression of scoliosis.
- Pancreatitis - Cases of pancreatitis have been reported rarely in children and adults receiving hGH treatment, with some evidence supporting a greater risk in children compared with adults. Pancreatitis should be considered in any hGH-treated subject, especially a child, who develops persistent severe abdominal pain.

AEs may include:

- Clinically significant treatment-emergent physical examination abnormalities
- Out-of-range lab or test results associated with new/worsening diagnosis, clinical sign, or symptom; or that require therapy

In this trial, all AEs that are considered mild and not related to investigational product will not be recorded on the AE CRF; this is with the exception of site-specific reporting preferences. In addition, the following out-of-range laboratory values—whether or not associated with a titration of the TransCon hGH dose—will not be considered AEs unless they are associated with a sign or symptom: IGF-1, IGF-1 SDS, IGFBP3, IGFBP3 SDS. In this trial, IGF-1 and IGFBP3 are pharmacodynamic markers of TransCon hGH therapy and may be used to guide an investigator's recommendation to titrate the TransCon hGH dose.

The Medical Expert will review all safety information on an ongoing basis. The key safety data will also be reviewed periodically by an ISC in accordance with its governing charter.

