12.1.2. Severity, Causality, and Outcome Assessment

12.1.2.1. Severity Rating

The following guideline must be used by the investigator to grade the intensity of an AE:

Mild – The subject is aware of the sign or symptom but tolerates it easily. The event is of little concern to the subject and/or of little or no clinical significance. The event is not expected to have any effect on the subject's health or well-being. The event may or may not require medical intervention.

Moderate – The event causes the subject enough discomfort for it to cause interference with or change some of the subject's usual activities. The event is of some concern to the subject and poses some risk to the subject's health or well-being. The event may require medical intervention.

Severe – The subject is incapacitated and unable to work or participate in many or all usual activities. The event is of definite concern to the subject and/or poses substantial risk to the subject's health or well-being. The event is likely to require medical intervention and/or close follow-up.

Life-threatening – The subject is at immediate risk of death from the event as it occurred.

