12.2. SERIOUS ADVERSE EVENTS AND SUSPECTED UNEXPECTED SERIOUS ADVERSE REACTIONS

12.2.1. Definitions

12.2.1.1. Serious Adverse Event Definition

In addition to severity and causality ratings, each AE is to be classified by the investigator as “serious” or “not serious.”

An SAE is any untoward medical occurrence that:

- Results in death
- Is life-threatening

Note: The term “life-threatening” here refers to an event in which the subject was at risk of death at the time of the event. It does not refer to an event which hypothetically might have caused death if it were more severe.

- Requires inpatient hospitalization or prolongation of an existing hospitalization

Note: Hospitalization for an elective procedure, for a routinely scheduled treatment, or scheduled in advance of trial participation are not considered SAEs.

- Results in persistent or significant disability/incapacity, or disruption of the ability to conduct normal life functions
- Is a congenital anomaly/birth defect

Note: This applies if a subject exposed to an investigational product gives birth to a child with a congenital anomaly or birth defect.

- Is an important medical event

Important medical events that may not result in death, be life threatening, or require hospitalization may be considered serious when, based upon appropriate medical judgement, they may jeopardize the subject or may require intervention to prevent one of the outcomes listed in this definition.

Events **not** considered to be SAEs are hospitalizations for:

- Routine treatment or monitoring of the investigational product or indication under study not associated with any deterioration in condition

- Treatment that was elective or planned prior to enrollment for a pre-existing condition unrelated to the investigational product or indication under study that has not worsened
- Admission to a hospital for general care not associated with any deterioration in condition
- Treatment on an emergency outpatient basis for an event not fulfilling any of the definitions of serious given above and not resulting in hospital admission

Suspected Unexpected Serious Adverse Reaction Definition

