12.2.2. Reporting

All initial and follow-up information regarding SAEs or SUSARs must be reported by the investigator to the Sponsor or its representatives within 24 hours of discovery, including those related to protocol-mandated procedures and regardless of suspected causality. Reporting must not be delayed by waiting for additional information. The minimum information required for reporting an SAE are the AE term (diagnosis) and the investigator’s initial causality assessment. Additional information can be reported to the Sponsor or its representatives as a follow-up report.

The Sponsor (or its representatives) is responsible for reporting within the time frame required by applicable regulations all SUSARs to:

- Investigators
- Central IRBs/HRECs/IECs
- National ethics committees (if applicable)
- Appropriate regulatory authorities

It is the investigators’ responsibility to comply with the requirements of their local IRB/HREC/IEC for reporting SUSARs, other SAEs, and any new and/or relevant safety information provided by the Sponsor or its representatives. At minimum, SUSARs must be brought to the attention of these review boards in accordance with regional regulations.

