- ¹¹ For subjects who were treated with Genotropin in the prior TransCon hGH CT-301 trial, C&OS-P, CSDS-P, CSDS-C, PQ-P, and PQ-C will be completed (as applicable) within the subject diary immediately prior to the 6th dose of investigational product, and in clinic at Visit 2, prior to review of the subject diary, AEs, and concomitant medications. For subjects transitioning to the GH Auto-Injector, C&OS-P, CSDS-P, and CSDS-C will be completed (as applicable) within the subject diary immediately prior to the 6th dose after transition to the GH Auto-Injector, and again in clinic at the following scheduled visit, prior to review of the subject diary, AEs, and concomitant medications. Additionally, for subjects transitioning to the GH Auto-Injector, the DUQ will be completed within the subject diary on the day of the 6th dose of investigational product, and in clinic at Visit 2, prior to review of the subject diary, AEs, and concomitant medications.
- ¹² CSDS-C and PQ-C should only be completed by subjects \geq 9 years old at the time of Visit 1, and/or at the transition to the GH Auto-Injector, as applicable.
- ¹³ Dose adjustments at visits are typically based on subject weight at visits. However, dose adjustments may occur between visits per Section 9.6.
- ¹⁴ Local tolerability assessment at the injection site to be performed at time of injection, and by the trial staff at visits.
- ¹⁵ Investigational product compliance includes review of subject diary and returned investigational product.
- ¹⁶ AE review includes review of subject diary and physical examination of injection sites. AEs that are considered mild and not related to investigational product will not be reported on the AE CRF. AEs reported up to 14 days after the final dose of TransCon hGH will be captured.

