- 11 For subjects who were treated with Genotropin in the prior TransCon hGH CT-301 trial, C&OS-P, CSDS-P, CSDS-C, PQ-P, and PQ-C will be completed (as applicable) within the subject diary immediately prior to the 6th dose of study drug, and in clinic at Visit 2, prior to review of the subject diary, AEs, and concomitant medications. For subjects transitioning to the auto-injector, C&OS-P, CSDS-P, and CSDS-C will be completed (as applicable) within the subject diary immediately prior to the 6th dose after transition to the TransCon hGH auto-injector, and again in clinic at the following scheduled visit, prior to review of the subject diary, AEs, and concomitant medications.
- 12 CSDS-C and PQ-C should only be completed by subjects ≥ 9 years old at the time of Visit 1, and/or at the transition to the TransCon hGH auto-injector, as applicable.
- 13 Dose adjustments at visits are based on subject weight at visits. However, dose adjustments may occur between visits per Section 9.6.
- 14 Local tolerability assessment at the injection site to be performed at time of injection, and by the trial staff at visits.
- 15 Study drug compliance includes review of subject diary and returned study drug.
- 16 AE review includes review of subject diary and physical examination of injection sites. AEs that are considered mild and not related to study drug will not be reported on the AE CRF.

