8.1. Adverse Events

AE is defined as any untoward medical occurrence in a clinical investigation subject administered a pharmaceutical product and which does not necessarily have a causal relationship with the treatment. An AE can therefore be any unfavorable and unintended sign (including

abnormal laboratory finding), symptom, or disease temporally associated with the use of a medicinal (investigational) product, whether or not related to that product. An AE can arise with any use (e.g., in combination with another drug), route of administration, formulation, or dose, including an overdose.

An AE is considered treatment emergent, i.e., Treatment Emergent Adverse Event (TEAE), is any AE that was first occurred or worsened after the first dose in this extension study and before the end of study. If the AE has any missing start date, the rules stated in Section 5.2 will be applied to determine if it is treatment-emergent.

A serious AE (SAE) is SAE is any untoward medical occurrence that:

- Results in death
- Is life-threatening
- Requires inpatient hospitalization or prolongation of an existing hospitalization
- Results in persistent or significant disability/incapacity
- Is a congenital anomaly/birth defect

Summaries of incidence rates (frequencies and percentages) of individual TEAEs by MedDRA SOC and preferred term will be prepared. Such summaries will be displayed for all TEAEs, TEAEs by maximum intensity, and TEAEs by strongest relationship to study drug. In addition, related TEAE, non-related TEAE, TEAE leading to study drug discontinuation, and serious TEAE, by SOC, the preferred term and TEAE by preferred term will be also summarized. Especially, related includes definite, probable and possible relationship. Not-related includes unlikely/remote and unrelated/not related.

Each subject will be counted only once within each preferred term. If a subject experience more than one TEAE within a preferred term, only the TEAE with the strongest relationship or the maximum intensity, as appropriate, will be included in the summaries of relationship and intensity.

Data listing of AEs, TEAE leading to study drug discontinuation, serious TEAE will also be provided.

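### The rule keeping mild, unrelated AEs off the AE CRF states no exception for serious or treatment-ending events, so two SAP 8.1 tables may be incomplete

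*Protocol*

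**What the plan says.** The recording rule appears four times.

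- Protocol 12.1.3: "In this trial, all AEs that are considered mild and not related to investigational product will not be reported on the AE CRF".
- Protocol 12.1.1 gives the same rule and adds the only exception found anywhere: "this is with the exception of site-specific reporting preferences".
- Protocol 18.2, Schedule of Events, note 16: "AEs that are considered mild and not related to investigational product will not be reported on the AE CRF".
- SAP Table 1 (under Section 3.2), note 16: "AEs that are considered mild and not related to study drug will not be reported on the AE CRF".

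SAEs also have a separate reporting duty. Protocol 12.2.2 requires every SAE to go to the Sponsor within 24 hours, "including those related to protocol-mandated procedures and regardless of suspected causality".

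Among its AE summaries, SAP 8.1 plans "TEAE leading to study drug discontinuation, and serious TEAE" by system organ class and preferred term, with listings of both.

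**The concern.** Leaving out mild, unrelated, non-serious events can be a deliberate economy in a long extension trial. Nothing in either document gives a reason for leaving out events that are serious or that end treatment, yet no statement of the rule sets them apart. A site that followed the rule exactly could keep such an event off the AE CRF. This does not depend on the exception for local preferences in 12.1.1.

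Long-term safety is the primary objective, and the serious-TEAE and discontinuation-TEAE tables bear directly on it. If the AE CRF is their only source, both could be short by rule rather than by error, and ordinary data cleaning of the AE CRF would not reveal it.

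**Working it through.** The plan states no figure on this point, so the check sets the passages side by side.

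**1. Can an affected event exist?** Protocol 12.2.1.1 begins: "In addition to severity and causality ratings, each AE is to be classified by the investigator as" serious or not serious. Severity, causality and seriousness are therefore three separate ratings. Inpatient hospitalisation alone makes an event serious. For a mild event, Protocol 12.1.2.1 says: "The event may or may not require medical intervention". A short, unplanned, unrelated admission graded mild can meet all three definitions. Likewise, the action taken is recorded separately from severity, so a mild event can end treatment.

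**2. Does any statement of the rule exempt it?**

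| Place | Exception for local site preferences | Exception for serious AEs | Exception for AEs leading to discontinuation |
|---|---|---|---|
| Protocol 12.1.1 | Yes | No | No |
| Protocol 12.1.3 | No | No | No |
| Protocol 18.2, note 16 | No | No | No |
| SAP Table 1, note 16 | No | No | No |

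The protocol does write an override where it wants one: 12.1.3 requires every overdose to be documented whether or not it counts as an AE.

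**3. What is lost if the event is not on the form?** Protocol 12.1.3 lists the attributes kept for each reported AE. They include the action taken and the determination of seriousness, the fields one would use to select events for the two SAP tables. An event that is not entered has neither.

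**4. What other routes exist?**
- Serious events: the 24-hour report under 12.2.2 has no severity limit, so the Sponsor holds the event.
- Non-serious events that end treatment: the paragraph on these events in Protocol 12.2.1 asks for discussion with the Medical Expert where the situation permits. Protocol 8.2 puts the reason for trial discontinuation into the eCRF, and SAP 6.1 summarises reasons. That yields a disposition reason. It does not guarantee a coded event in the TEAE table, so the gap is more direct here than for SAEs.

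**5. Do the documents connect those routes to the tables?** SAP 8.1 names no data source. SAP 5 says that data collected on the eCRF will be listed, and SAP 4.2 refers to integrating the relevant study data into the analysis database. Neither document describes entering the 24-hour reports on the AE CRF, reconciling the two, or using the reports for the tables.

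**6. How wide is the affected set?** It needs mild, not related, and either serious or treatment-ending. The second condition is not sharply defined: Protocol 12.1.2.2 separates unlikely from unrelated, while SAP 8.1 counts both as not related. The wider reading would enlarge the set.

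**7. Scale.** One missing subject changes an incidence by 1/300 = 0.33 percentage points at the protocol's planned size, or 1/400 = 0.25 at the SAP's. As an illustration on assumptions not found in the documents: suppose 2% to 5% of 300 subjects have an SAE (300 × 0.02 = 6 to 300 × 0.05 = 15), and 0% to 20% of those have only mild, unrelated SAEs. Then 0 to 15 × 0.20 = 3 subjects would be missing, or 0 to 3/300 = 1.0 percentage point.

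**The case against.** The best reply is that the text is ambiguous rather than a rule that removes SAEs. Protocol 12.1.3 says that AEs, SAEs among them, are documented to the end of participation. It requires reportable AEs to be recorded whatever their causality, and it presents 12.2.2 as procedures added to AE recording. On a fair reading, an SAE is always reportable. The CRFs and the data management plan are not among the documents, and Protocol 15.5.2 says that plan will contain consistency checks, so a separate SAE form or a reconciliation step may exist. The overlap is also narrow. Protocol 12.1.2.1 describes a mild event as easily tolerated and not expected to affect health, 12.1.3 grades AEs at their worst intensity, and 12.2.1.1 excludes elective, pre-planned and routine admissions from SAEs.

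Most of this stands, and it limits the point. It does not close the gap. The word reportable is not defined, it follows the exclusion in the same paragraph, and nothing says that the SAE procedures override the CRF rule. Two sites could read it differently.

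A reader might go further and infer that these events are certain to drop out, or that the clinical and safety databases could not be reconciled. The documents support neither. The data flow is not described, and SAE reports that the Sponsor already holds can be compared with the AE CRF and entered.

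**Conclusion.** The gap is real and should be fixed, but it is not critical. No statement of the rule exempts serious AEs or AEs leading to discontinuation of study drug, and no link from the 24-hour SAE reports to the AE dataset is described. Read literally, a mild, unrelated event of either kind may be missing from its table in SAP 8.1. SAEs remain known to the Sponsor, and discontinuation reasons remain visible in disposition.

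Few events are likely to be affected. A reader might build a larger count from assumed SAE numbers and assumed shares that are mild and unrelated. The documents supply none of these, and any minimum mild share above zero builds in a loss that the definition of mild does not imply. The conclusion rests on the missing exception, and on the assumption that no unseen document already supplies the link.

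**What to change.** In Protocol 12.1.1, Protocol 12.1.3, Protocol 18.2 note 16 and SAP Table 1 note 16, add: *except serious AEs and AEs leading to discontinuation of investigational product, which are always recorded on the AE CRF regardless of severity or causality*. The exception need not extend to dose changes or interruptions, because SAP 8.1 plans no AE table for them.

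In SAP 8.1, state that the serious and discontinuation tables use AE data reconciled with the SAE reports. Before database lock, enter on the AE CRF any mild, unrelated SAE that the Sponsor already holds.

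The cost is one clause in four places, one sentence in SAP 8.1, and a small amount of back-entry and reconciliation work. Clinical management does not change.
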